Appendix B
Schedule of Assessment and Study Flow Chart

ASSESSMENTS	Screening and Baseline (Visit 1)	Study Drug Administration	22–36 Hours from Start of Study Drug Administration (Visit 2)	Day 5 (or Discharge if Sooner) (Visit 3)	30 Days (±7 Days) Phone Call (Visit 4)	90 Days (± 14 Days)/ Study Completion Visit (Visit 5)	Early Discontinuation (Phone call if possible)
Informed consent	X						
Review of eligibility	X						
Medical history and baseline conditions ^a	X						
Demographics	X						
Physical examination ^b	X						
Vital signs ^c	X						
Complete blood count ^d	X						
Coagulation status ^e	X						
Pregnancy test ^f	X						
Serum blood glucose ^g	X						
Imaging modality sensitive to presence of intracranial hemorrhage (either CT or MRI with DW MRI, either SW or GRE, and FLAIR images). Visit 2 MRIs should also include T1 and T2 sequences ^h	X		X				
NIHSS score ⁱ	X		X	X		X	
Study drug administration		X					

Statistical Analysis Plan: Alteplase—Genentech USMA
39/ML29093 5/17/2017

ASSESSMENTS	Screening and Baseline (Visit 1)	Study Drug Administration	22–36 Hours from Start of Study Drug Administration (Visit 2)	Day 5 (or Discharge if Sooner) (Visit 3)	30 Days (±7 Days) Phone Call (Visit 4)	90 Days (± 14 Days)/ Study Completion Visit (Visit 5)	Early Discontinuation (Phone call if possible)
Discharge location				X			
Patient survival			X	X	X	X	X
mRS ^j					X	X	
GOS						X	
BI ^k						X	
EQ-5D ^k						X	
CES-D ^k						X	
SIS-16 ^k						X	
Cognitive assessment ^l						X	
Walking speed ^m						X	
Concomitant medications ⁿ	X		X	X	X	X	X
Assessment of pregnancy					X		
Adverse event ^o	X		X	X	X	X	X

BI = Barthel Index; BNT =Boston Naming Test; CES-D = Centers for Epidemiologic Studies, Depression; CT =computed tomography; DW MRI= diffusion-weighted MRI; European Quality of Life = EQ-5D; FLAIR = fluid-attenuated inversion recovery; GOS = Glasgow Outcome Scale; GRE= gradient echo; HVLT-R=Hopkins Verbal Learning Test-Revised; ICH = intracranial hemorrhage; INR = international normalized ratio; MRI=magnetic resonance imaging; mRS modified Rankin Scale; NIHSS= NIH Stroke Scale; Stroke Impact Scale-16= SIS-16; SWMRI= susceptibility-weighted MRI; WAIS III =Wechsler Adult Intelligence Scale III.

^a Includes smoking history and stroke history.

^b A partial neurological examination is to be performed for each patient. The NIHSS will be a component of the neurological examination and will be performed only by practitioners who are certified to perform an NIHSS assessment. Additional, or supplemental, neurological exams will also be performed, including assessment of mental status, cranial nerves, motor function and coordination.

Statistical Analysis Plan: Alteplase—Genentech USMA

40/ML29093

[figure not shown]
5/17/2017

ASSESSMENTS	Screening and Baseline (Visit 1)	Study Drug Administration	22–36 Hours from Start of Study Drug Administration (Visit 2)	Day 5 (or Discharge if Sooner) (Visit 3)	30 Days (±7 Days) Phone Call (Visit 4)	90 Days (± 14 Days)/ Study Completion Visit (Visit 5)	Early Discontinuation (Phone call if possible)
-------------	----------------------------------	---------------------------	---	--	--	---	--

- ^c Includes pulse and systolic/diastolic blood pressure (while patient is in a supine position).
- ^d Complete blood count includes hemoglobin, hematocrit, white blood cell count, and platelet count.
- ^e Coagulation status includes INR values of > 1.7, activated partial thromboplastin time, patient or family report of patient currently taking an oral anticoagulant (e.g., dabigatran, rivaroxaban, apixaban, edoxaban), or patient or family report of patient currently taking a low-molecular-weight heparin (e.g., dalteparin, enoxaparin) within the last 48 hours.
- ^f Pregnancy status will be determined in women of childbearing potential. Serum or urine pregnancy test can be collected.
- ^g Serum glucose (values of < 50 mg/dL are contraindicated for alteplase).
- ^h MRI or CT scan should be performed if any clinical findings suggest ICH.
- ⁱ NIHSS score should be assessed and recorded at the time of any clinical findings that suggest ICH.
- ^j The mRS may be performed by telephone, if necessary, for visits on Days 30 and 90.
- ^k The BI, CES-D, EQ-5D, and SIS-16 can be administered by phone interview if an in-person patient visit cannot be scheduled in the allotted time.
- ^l Assessments include: Controlled Oral Word Association test; HVLT-R trials 1, 2, and 3; digit symbol coding from the WAIS III; Forward and Backward Digit Span test; Benton Judgment of Line Orientation, form V; HVLT-R trial 4 and recognition; semantic fluency (Animal Naming test); and BNT (15-item short form).
- ^m Assessment of walking speed requires an in-person patient visit and is best combined with administration of the BI, CES-D, EQ-5D, and SIS-16.
- ⁿ Concomitant medications include any prescription medications or over-the-counter preparations used by the patient within 7 days prior to screening.
- ^o Adverse event assessments will be performed during study drug administration; at 22–36 hours after study drug administration; on Days 5, 30, and 90 (may be done via telephone interview if necessary), and at early discontinuation. Refer to Section 5.3.1 (Adverse Event Reporting Period) for further details.

Statistical Analysis Plan: Alteplase—Genentech USMA
41/ML29093 5/17/2017

Figure 1 Study Flowchart

ASA = aspirin; CT= computed tomography; IV = intravenous; MRI = magnetic resonance imaging; mRS=modified Rankin Scale; NIHSS = National Institutes of Health Stroke Scale.

Appendix C Randomization Scheme

Initialization of the algorithm:

- Generate a randomization list for all sites such that half the sites receive Treatment Arm A, half the sites receive Treatment Arm B as the first treatment assignment. Need to ensure that as each SITE is activated there is balance between Treatment Arm A and Treatment Arm B after every x sites have been activated (ie., use permuted block randomization with block size of x)
- At the time of drug supply receipt verification, obtain the first "USE NEXT" treatment assignment sequentially from the pre-generated randomization list. When the "USE NEXT" treatment assignment is used on a patient or wasted, then the next "USE NEXT" treatment assignment is according to the algorithm in Steps 1 and 2.

Note: If this assignment has not been done in time for the next patient's arrival to the site, then the new patient will be randomized by a fair coin flip. This will be achieved by calling IWRS technical support.

1. Identify the site for which the "USE NEXT" kits are to be assigned (Let "j" be the site number).
2. Calculate the intermediate variables needed (see [Table 4](#)) and update the appropriate data set.
3. Compare the appropriate intermediate variables to the specified threshold values, site first then overall (see [Table 5](#)).
4. IWRS Service Provider will update the appropriate dataset with (a) USE NEXT numbers, (b) random number used by algorithm, (c) study-specific algorithm step at which treatment was determined.
5. When patients have been treated with study drug kits and registered in the system, IWRS updates the enrolled numbers and USE NEXT kit numbers.

[Figure 2](#) displays the randomization steps for the step-forward randomization.

Table 4
Intermediate Variables for the Next Allocation Probability

[figure not shown]
Variable	Definition
S _j _A	Number of enrolled patients in Treatment Arm A at Site j
S _j _B	Number of enrolled patients in Treatment Arm B at Site j
S _j _AB	Imbalance between treatment arms in enrolled patients at Site j, S ₁ _A - S ₁ _B
S _j _Min	Minimum number of enrolled patients in the two treatment arms at Site j, S _j _Min = min(S _j _A, S _j _B)
S _j _PA	Probability for assigning the use next kits to treatment arm A in Site j, S _j _PA = (S _j _Min - S _j _A + MTI-C) / (2*S _j _Min - S _j _A - S _j _B + 2*MTI-S)
O_A	Number of enrolled (ie, treated) patients in Treatment arm A
O_B	Number of enrolled patients in Treatment arm B
O_AB	Overall imbalance between treatment arms in enrolled patients, O_A - O_B, directionality required

Table 5
Decisions Based on Site and Overall Imbalance

Step	Site Threshold Comparison	Type of Assignment	USE NEXT Kit Assignment
1	If S _j _AB <= -MTI-S	Deterministic	Treatment Arm A.
	If S _j _AB >= + MTI-S	Deterministic	Treatment Arm B.
	if -MTI-S < S _j _AB < + MTI-S		Go to STEP 2
2	If S _j _PA = 0.5		Check overall imbalance, O_AB
	If O_AB <= -MTI-O	Probabilistic	Treatment Arm A with probability P_BC
	If O_AB >= + MTI-O	Probabilistic	Treatment Arm A with probability 1 P_BC
	If S _j _PA ne 0.5		Treatment Arm A with probability S _j _PA

Note: MTI-S is the site threshold level (ie, x). MTI-O is the overall threshold level (ie, y). P_BC is the biased coin probability (ie, 0.75).

Figure 2 Study Randomization Schema

Appendix D

Statistical Methods Requiring Input

Handling of incomplete start and stop dates of adverse events

A missing day in a start date will be imputed with the first day of the month, but not earlier than the randomization date. A missing day in a stop date will be imputed with the last day of the month.

A missing month/year in a start date will be imputed by the month/year of randomization. A missing month in a stop date will be imputed by the month of the last contact. A completely missing stop date will be treated as an ongoing AE and will not be imputed.

Determination of ICH and sICH events

For ICH and sICH events, the following rules will be used to determine their timing relative to 36 hours:

- For ICH determination by scan reading (local or central), take the earliest post-baseline scan with bleeding identified. Use the evaluation time of that scan to compare to 36 hours.
- For ICH determination by AE reporting, take the start date of the corresponding AE. Then find all scans with the same date of local reading, where bleeding is identified. Take the earliest such scan and use the evaluation time of that scan to compare to 36 hours. If no scan is found, use 12:00 am on the AE start date to compare to 36 hours.

When there are multiple scans associated with a PH2 bleed in a subject, the first of these scans will be used to select pre- and post-scan NIHSS scores.

Logistic regression with correlated measures

This model will be used to estimate the odds ratio describing the global favorable outcome, and to estimate the odds ratio of achieving mRS 0-1 at Day 90 in the context of repeated measures.

Statistical Analysis Plan: Alteplase—Genentech USMA
46/ML29093 5/17/2017

The model is specified as follows:

- Let Y_{ik} , be the correlated binary outcomes (1 = favorable outcome, 0 = unfavorable outcome) for patient i , and let $E(Y_{ik}) = \mu_{ik}$ be the marginal means of the outcomes conditional on the patient-specific covariates, including treatment.

For the analysis of the global favorable outcome, $k=1, \dots, 4$ will index the 4 dimensions (mRS, NIHSS, BI, and GOS).

For the analysis of mRS 0-1 $k=1, 2$ will index the repeated evaluations of mRS (Day 30 and Day 90).

- The linear predictor will include an outcome-specific intercept α_k , treatment T_i , and the explanatory variables X_i . The link function transforming the marginal mean outcome μ_{ik} into the linear predictor will be the logit function:

$$\text{logit}(\mu_{ik}) = \alpha_k + \beta T_i + \gamma_k X_i$$

Importantly, it will be assumed that all outcomes share the same treatment effect β .

- The variance function of Y_{ik} will be determined by the binary distribution variance:

$$\text{Var}(Y_{ik}) = \mu_{ik}(1 - \mu_{ik})$$

- The working correlation matrix structure for the outcomes from the same patient will be assumed to be unstructured:

$$\text{Corr}(Y_{ik}, Y_{im}) = \rho_{km}, k \neq m$$

For the repeated measures model of mRS 0-1, a temporal correlation structure may be chosen instead, which takes into account the distance in time between the repeated measures:

$$\text{Corr}(Y_{i1}, Y_{i2}) = \rho^{|d1-d2|},$$

where $d1$ and $d2$ are study days of Day 30 and Day 90 assessments.

Estimation will be carried out by the generalized estimating equations (GEE).

Adjusted Risk Difference with logistic regression

The logistic regression model defined for the mRS 0-1 outcome provides estimates of the odds of a favorable outcome. These odds can then be converted to probabilities, and thus the risk difference can be obtained as a non-linear contrast

Statistical Analysis Plan: Alteplase—Genentech USMA
47/ML29093 5/17/2017

between the treatment groups. Linearization of this contrast provides an estimate of the standard error, the approximation known as the delta method.

This approach can be implemented with SAS PROC NLMIXED. Here is a sample code:

```
proc nlmixed data=MRS;
  eta=b0+b1*(TRTPN=1)+b2*AGE+b3*OTT+b4*NIHSS;
  p=1/(1+exp(-eta));
  model respn ~ binomial(1,p);
  estimate "tPA vs. Aspirin"
    1/(1+exp(-(b0+b1+b2*&m1+b3*&m2+b4*&m3)) -
    1/(1+exp(-(b0+b2*&m1+b3*&m2+b4*&m3)));
run;
```

where TRTPN=1 selects tPA treatment, and macro variables m1, m2 and m3 resolve to the mean values of AGE, OTT and NIHSS, respectively.

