2.2.4 Safety Outcome Measures

The safety outcome measures for this study are as follows:

- Symptomatic Intracranial Hemorrhage (sICH) within 36 hours of receiving IV study drug (primary safety assessment)

sICH is defined as any neurological decline attributed to new ICH seen on imaging by the investigator (based on AE reporting). New ICH seen on imaging will be later confirmed on independent reading by blinded central study radiologists
- Any ICH (based on central neuroimaging reading) within 36 hours of receiving IV study drug
- Mortality within 90 days

Statistical Analysis Plan: Alteplase—Genentech USMA
7/ML29093 5/17/2017

- Stroke-related and neurological deaths within 90 days
- Incidence, severity, and spectrum of all adverse events (AEs) and serious AEs (SAEs).

The exploratory safety measure for this study is:

- Stroke recurrence (based on AE monitoring) within 90 days

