4.6.3 Neuroimaging

Neuroimaging may consist of a non-contrast computed tomography (CT) or magnetic resonance imaging (MRI) of the brain. Non-contrast CT or MRI will be performed at baseline to ensure that the patient does not have evidence of acute intracranial hemorrhage (ICH) prior to study drug administration.

An additional non-contrast CT or MRI will be performed at 22 to 36 hours from the initiation (bolus) of study drug infusion. The purpose of this is to evaluate for ICH in the patient. Additional CT scans or MRIs should be performed based on the investigator's discretion, or if any clinical findings suggest ICH.

All CT and MRI scans will be evaluated by a central team of radiologists blinded to the clinical attributes of the case. Results from the evaluation of the CT or MRI scans by both local and central readings will be listed, as available.

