4.6.3.1 Intracranial Hemorrhage

Intracranial hemorrhage events (ICH) are identified by neuroimaging and are recorded as AEs using one of the terms specified in protocol Appendix 13. The images obtained within the first 36 hours after treatment are further evaluated by central reading, which may or may not confirm ICH.

While ICH may be identified at any time during the study, the first 36 hours after treatment are the key time interval. If multiple scans indicate ICH within 36 hours, it is interpreted as a single ICH event. ICH events identified after the first 36 hours will contribute to the general AE summaries. Timing of ICH will be determined according to the rules specified in [Appendix D](#).

Incidence of ICH within 36 hours by AE reporting will be presented by treatment group. Determination of ICH within 36 hours from local and central readings of scans will also be presented, and agreement between the local and central readings will be tabulated.

Difference in percentage of subjects with ICH within 36 hours based on central and local scan reading will be reported by treatment group. A two-sided 95% CI around this difference will be constructed using the Miettinen-Nurminen score method (20).

Additionally, central reading classifications will be used to further describe subtypes of any ICH.

The central reading will classify ICH according to the following intracerebral subtypes:

- Hemorrhagic infarct type 1 or type 2
- Parenchymal hematoma type 1 or type 2
- Remote intraparenchymal hemorrhage type 1 or type 2

In addition, subarachnoid hemorrhage, subdural hemorrhage, or epidural hemorrhage will be noted. ICH subtypes will be tabulated by treatment group.

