4.6.3.2 Symptomatic Intracranial Hemorrhage

The protocol specifies that ICH is considered symptomatic (sICH) if it is not seen on CT or MRI scan at baseline, and any neurologic decline is attributed to it by the local

investigator. Both serious sICH and non-serious sICH events are required to be reported by the investigator to the Sponsor immediately.

sICH within 36 hours is considered the primary safety outcome. sICH events are captured through AE reporting.

In addition to the primary definition of sICH, the following two definitions of sICH will be explored and reported in this study.

- sICH using Heidelberg classification: either (1) PH2 as reported by radiology core, or (2) an sICH as classified by PRISMS but also associated with 4-point total NIHSS score worsening or 2 point worsening on any single NIHSS item when comparing scores immediately pre and post scan.
- sICH using SITS-MOST definition (25): PH2 as listed by radiology core on CT scan between 22-36 hours, which is associated with deterioration of ≥ 4 points on the NIHSS from the lowest NIHSS value between baseline and 36 hours, but prior to repeat CT, or leading to death.

Percentage of subjects with sICH within 36 hours will be presented for each definition by treatment group. Difference between treatment group percentages will be reported along with a two-sided 95% CI constructed using the Miettinen-Nurminen score method (20).

ICH symptomatology will be tabulated for confirmed strokes and separately for stroke mimics.

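### Appendix D can place AE-reported intracranial hemorrhage on the wrong side of 36 hours, because scans are matched by local reading date with a midnight fallback and the scan time used is not defined

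*SAP*

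**What the plan says.** Section 2.2.4 sets the window for the primary safety outcome: "Symptomatic Intracranial Hemorrhage (sICH) within 36 hours of receiving IV study drug (primary safety assessment"). Section 4.6.3.2 confirms its rank ("sICH within 36 hours is considered the primary safety outcome") and says that these events are captured through AE reporting.

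Appendix D, under the determination of ICH and sICH events, gives two timing rules.

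- **ICH by scan reading, local or central.** Take the earliest post-baseline scan showing bleeding, then: "Use the evaluation time of that scan to compare to 36 hours".
- **ICH by AE reporting.** Start from the AE start date. "Then find all scans with the same date of local reading, where bleeding is identified". The earliest of these supplies the time. Otherwise: "If no scan is found, use 12:00 am on the AE start date to compare to 36 hours".

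Section 4.6.3 schedules the follow-up scan: "An additional non-contrast CT or MRI will be performed at 22 to 36 hours from the initiation (bolus) of study drug infusion". Section 4.6.3.1 describes the central-reading window by when images were acquired: "The images obtained within the first 36 hours after treatment are further evaluated by central reading, which may or may not confirm ICH".

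Section 4.6.3.2 also lists two additional sICH definitions to be explored. The SITS-MOST one requires "PH2 as listed by radiology core on CT scan between 22-36 hours".

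**The concern.** The AE rule links an event to a scan through two dates that need not agree: the day the AE began and the day the local reader read the scan. A patient who worsens late in the evening and whose scan is read after midnight has a documented bleed with a known time, and the rule ignores it in favor of a time that can be almost 24 hours before onset. Section 4.6.3.1 says that ICH is identified by neuroimaging, so a usable scan should normally exist.

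The scan rule rests on the term *evaluation time*, which the SAP does not define. Section 4.6.3 uses the same verb for the central radiologists' reading, while Section 4.6.3.1 speaks of images acquired within 36 hours. The scheduled scan may be taken right up to the cut-off, so there is no slack for a reading delay. Two programmers could derive different counts from the same data.

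With 313 patients randomized and bleeding events likely to be few, one event on the wrong side of the cut-off shows in the risk difference and its interval.

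**Working it through.** The SAP gives no figure to reproduce here, so the check is the arithmetic of the rules.

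**Inputs from the SAP.** Cut-off 36 h from receipt of IV drug (Section 2.2.4). Scheduled scan at 22–36 h (Section 4.6.3). 313 randomized (Section 2.3), so about 156 per arm at 1:1. **Assumptions, not in the SAP:** clock time of dosing, reading delay, and uniform distributions where stated.

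**1. Midnight fallback.** Let T be the clock time of the dose in hours (0 to 24) and e the true onset in hours after the dose. The AE falls on calendar day d = floor((T + e)/24), counting the dosing day as 0. The fallback assigns m = 24d − T, and the event counts if m ≤ 36.

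- Dose before noon (T < 12): d = 0 or 1 counts, so the latest true onset counted is 48 − T. This is 42 h for a 06:00 dose and 40 h for an 08:00 dose.
- Dose at or after noon (T ≥ 12): d = 2 also counts, so the latest true onset counted is 72 − T. This is 60 h for a 12:00 dose, 58 h for 14:00 and 52 h for 20:00.
- Since m ≤ e always, no true event at or before 36 h is lost.
- For an AE on the dosing day, d = 0 and m = −T, which is before the dose.

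*Illustration.* Dose at 14:00 on Monday, onset at 23:00 on Wednesday (10 + 24 + 23 = 57 h), bleeding scan read at 00:30 on Thursday (58.5 h). No bleeding scan was read on Wednesday, so the event is timed at 00:00 on Wednesday: 48 − 14 = 34 h. It counts as within 36 h.

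**2. Share of unmatched late AEs pulled inside.** Take T uniform over 24 h and e uniform in the band.

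- True onset 36–48 h: for T < 12 the share is (12 − T)/12, which averages 0.5; for T ≥ 12 it is 1. Overall 0.5 × 0.5 + 0.5 × 1 = 75%.
- True onset 48–60 h: for T < 12 it is 0; for T ≥ 12 it is (24 − T)/12, which averages 0.5. Overall 0.5 × 0.5 = 25%.
- Dosing between 08:00 and 20:00 instead: (1/3)(2/12) + (2/3)(1) = 72% and (2/3)(8/12) = 44%.

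A simulation with 1,000,000 draws gave the same values. They apply only to AEs that have no same-date bleeding scan and truly began after 36 h.

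**3. *Evaluation time* taken as reading time.** With scans uniform over the 14-hour window from 22 to 36 h, a reading delay of L hours pushes a share L/14 past the cut-off:

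| Delay | Scans pushed past 36 h |
|---|---|
| 0.5 h | 4% |
| 1 h | 7% |
| 2 h | 14% |
| 4 h | 29% |
| 14 h or more | 100% |

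Taken as acquisition time, the share is zero.

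**4. Weight of one event.** 1/156 = 0.64 percentage points. For scale only, since the SAP gives no event counts, the planned Miettinen-Nurminen 95% interval with 156 per arm is:

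| Events, alteplase v aspirin | Difference (points) | 95% CI |
|---|---|---|
| 3 v 0 | 1.9 | −0.5 to 5.5 |
| 4 v 0 | 2.6 | 0.1 to 6.4 |
| 4 v 1 | 1.9 | −1.2 to 5.9 |

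One event added to or removed from either arm can decide whether the interval excludes zero.

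**The case against.** **Midnight is only a fallback.** It applies when no bleeding scan shares the AE date. ICH is found by imaging and then recorded, so the two dates should usually agree. The rule works from a date without a time and needs some convention, and one that errs toward inclusion is cautious for a harm. Most of this stands: the rule loses no true early event, and mismatches may be uncommon. But inclusion is not cautious for a between-arm difference, because an event wrongly added to the aspirin arm shrinks the apparent excess. Nor is a convention needed when a timed bleeding scan exists.

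**The scan time may well mean acquisition.** The AE rule uses a separate phrase for the local reading date, and one scan time serves local and central reads alike, which fits a property of the scan. The SAP also plans a centrally read 36-hour outcome, which would make little sense if timed by later reading. Appendix F defers data handling rules to a separate document, where the term could be fixed. This is strong. A reader might infer that the rule empties the central-read outcome; the SAP does not support that, because it never equates the term with reading time. What remains is an undefined term at the decisive step.

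**The SITS-MOST row.** A reader might infer that its limit to CT at 22–36 h distorts the primary outcome. It does not. It is one additional, exploratory, externally cited definition; the primary definition covers CT and MRI, and the Heidelberg row accepts a core-read PH2 with neither limit. Widening it would alter a named definition.

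**Visibility.** ICH within 36 h is shown by AE, local and central reading, with agreement tabulated, so many discordant cases would be seen. But sICH is captured through AE reporting, and a visible discrepancy still needs a rule.

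**Conclusion.** The point holds in a limited form. The AE-matching rule, as written, can give a wrong answer for the primary safety outcome: when onset and reading fall on different dates, a known bleeding scan is ignored and an event truly at up to 60 h can count as within 36 h. This follows from the rule alone; only the shares of 75% (36–48 h) and 25% (48–60 h) need the uniform dosing-time assumption, and they are conditional on an unmatched, truly late AE. They are not misclassification rates for the trial. The error from *evaluation time* is conditional on the term being programmed as reading time, and it would then act the other way, removing events. The two errors do not cancel, because they affect different events.

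It would go too far to say that bleeding outcomes are misclassified. The SAP gives neither the frequency of date mismatches nor the event counts, so the effect on the result is unknown beyond 0.64 points per moved event. This should be fixed; it is not a must-fix.

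**What to change.** In Appendix D:

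1. State that the 36-hour comparison uses the acquisition date and time of the scan, for local and central reads alike.
2. Match each AE-reported ICH or sICH to the bleeding-positive post-baseline scan closest to the AE start date, for example within one day either way, instead of requiring the same local reading date.
3. Use midnight of the AE start date only if no bleeding scan exists, and flag those cases in the listing. State how a fallback time before the dose is handled, so that a same-day AE is not dropped by a check for negative times.

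In Section 4.6.3.2, keep the SITS-MOST definition as cited. At most, add a footnote that, as written, it counts only PH2 on CT at 22–36 h, so bleeds seen only on MRI or only on earlier scans do not enter that exploratory row.

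The cost is a few lines of SAP text and a change to the derivation code before unblinding, provided that scan acquisition times were collected, which the SAP does not confirm. No new data, visits or analyses are needed.
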